3.5 Sample Size and Power Considerations

Seventy-two subjects per treatment group in the ITT population will yield 90% power at a significance level of 0.05 (two-sided) using a two-sample t-test with equal allocation to the treatment

groups. This assumes an effect size of 0.547, observed in the comparison of SPN-812 200 mg and placebo in the SPN-812 Phase IIb study (based on the CFB to endpoint in the ADHD-RS-IV total score). A total of 300 subjects (100 subjects in each of the three treatment groups) will be randomized to account for an anticipated 27.9% of randomized subjects not completing the study.

4 Definitions and Derivations

1. Baseline: Unless specified otherwise, baseline is defined as the non-missing value collected most recent to and before the time of the very first dose of the SM.
2. The study day (DY) is calculated as Visit date minus Reference date + 1 day if the visit date occurs on or after the reference date or Visit date minus Reference date if the visit date occurs before the Reference date, where the Reference date is defined as the first dose date (DY=1)
3. The change from baseline at a given Visit = observed value at that Visit minus observed value at baseline
4. ADHD-RS-5 total score =sum of scores for the 18 behaviors
5. ADHD-RS-5 Inattention subscale score = sum of scores for the first 9 behaviors
6. ADHD-RS-5 Hyperactivity/Impulsivity Subscale score = sum of scores for the last 9 behaviors
7. Conners 3-Parent Reported score: Composite T-score calculated by averaging over the 6 domains
8. Conners 3-Parent Reported score: T-score for individual domain: inattention, hyperactivity/impulsivity, aggression, executive functioning, learning problems, and relationships
9. Conners 3-Self Reported score domains: Composite T-score over the 5 domains
10. Conners 3-Self Reported score domains: inattention, hyperactivity/impulsivity, aggression, learning problems, and relationships
11. WFIRS-P score=average of all 50 items
12. WFIRS-P subscale scores: average of items of following 6 subdomains: Family, School (learning and behavior), Life Skills, Child's Self-Concept, Social Activities, and Risky Activities
13. PSI-4-SF: score=sum of all 36 items
14. PSI-4-SF: subscale scores: sum of items of following 3 subdomains: parental distress (PD), parent-child dysfunctional interaction (P-CDI), and difficult child (DC)

5 Study Variables

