5.2 Secondary Efficacy Variables

5.2.1 Clinical Global Impression-Improvement

The CGI scale was developed to provide a brief, stand-alone assessment of the clinician's view of a subject's global functioning prior to and after administration of a SM ([Guy 1976](#)). The Clinical Global Impression – Severity of Illness (CGI-S) is a single item clinician rating of clinician's assessment of the severity of the ADHD symptoms in relation to the clinician's total experience with patients with ADHD. The Clinical Global Impression – Improvement Scale (CGI-I) is an assessment of how much the patient's illness has improved or worsened relative to a baseline state at the beginning of treatment. Both CGI-S and CGI-I are rated on a 7-point scale of 1 to 7 with 7 being "extremely ill" or "very much worse", respectively. Successful therapy is indicated by a lower overall score in subsequent testing.

CGI-I, relative to the condition at baseline, will be evaluated by the Investigator at each post-baseline visit on a 7-point scale with 1=Very much improved, 2=Much improved, 3=Minimally improved, 4=No change, 5=Minimally worse, 6=Much worse, and 7=Very much worse.

5.2.2 Conners 3

The Conners 3rd Edition™ (Conners 3) is a focused diagnostic tool for assessment of ADHD and associated learning, behavior, and emotional problems in children ages 6 to 18 years ([Sparrow, 2010](#)). The scale is based on the solid findings and key elements of its predecessor, the Conners Rating Scales-Revised (CRS-R™), but offers a more refined assessment of ADHD and comorbid

disorders (e.g., oppositional defiant disorder and conduct disorder). The Conners 3 instrument includes items related to inattention, hyperactivity, and impulsivity, as well as assessments of executive functioning, learning problems, and relationships. Like previous versions, the Conners 3 combines teacher, parent, and student reports to provide a particularly detailed and comprehensive evaluation of student behavior as observed in different settings. Teacher, parent, and self-report (for 8-18y.o.) rating scales are all available in long and short versions. The short forms of Parent, Teacher, and Self Reports of Conners 3 are comprised (respectively) of 45, 41, and 41 items. All Conners 3 scale versions are scored on a 4-point scale (0-3), where a higher score indicates more severe symptom presentation.

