6.13 Efficacy Analyses

The efficacy analyses will be based on the ITT population and will be performed on ADHD-RS-5 total score, Conners 3-PS composite T score, Conners 3-SRS composite T score, WFIRS-P total score and PSI-4-SF total scores.

All confidence intervals, statistical tests, and resulting p-values will be reported as two-sided and will be assessed at the 5% significance level and interactions at 10%.

With respect to Analysis of Covariance, the Gamma regression will be used on the original scale, if the normality assumption for the standard ANCOVA model is not met based on diagnostic residual plots based on the data before imputation.

Multiplicity will be adjusted for the primary endpoint and key secondary endpoints.

The mean profiles of ADHD-RS-5 total score, Conners 3-PS composite T score, Conners 3-SRS composite T score, WFIRS-P total score, PSI-4-SF score and CGI-I score will be presented graphically by treatment group and scheduled study visit. In addition, plots of the Cumulative Distribution Functions of Change from Baseline in ADHD-RS-5 will be presented (Figures 14.2.1.1 - 14.2.6.2)

For supportive analysis, the absolute value and change from baseline to Week 8 (EOS) of all efficacy variables will be summarized using descriptive statistics by treatment group and visit (Tables 14.2.5.1- 14.2.5.6).

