6.14.1.1 Clinical Global Impression – Improvement (CGI-I)

The absolute value of CGI-I at week 8(EOS) will be analyzed using ANCOVA with treatment as a fixed classification variable and baseline CGI-S as a covariate. This ANCOVA analysis supersedes the ANOVA analysis described in the protocol. Each of the treatment groups (SPN-812 ER 200 mg and 400 mg) will be compared with the Placebo. The p-values, Least Squares means of the treatment groups, differences between the LS treatment means and placebo (SPN-812 ER 200 mg minus Placebo and SPN-812 ER 400 mg minus Placebo), 95% confidence intervals for the treatment differences will be computed. The summary of this analysis will be presented in Table 14.2.2.1.1 and listed in Listings 16.2.6.3.2- 16.2.6.5.

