6.14.1.2 Conners 3-Parental Short Form

The Conners 3-PS will include 6 domains (subscales): inattention, hyperactivity/impulsivity, aggression, executive functioning, learning problems, and relationships.

The data for Conners 3-PS comprise derived T-scores for each domain rounded to the nearest integer. If a T-score ≤ 40 then the T-score will be set to 40 and if a T-score ≥ 90 then the T-score will be set to 90. If 1 of the subdomains is missing then the total score will be missing and the missing value will be handled using multiple imputation under MAR. A composite T-score will be calculated by averaging over the six domains (rounded to the nearest integer) and the change from baseline to Week 8 (EOS) in the composite T-score will be analyzed using ANCOVA model with fixed classification variable for treatment and baseline as a covariate. Each of the treatment groups

(SPN-812 ER 200 mg and 400 mg) will be compared with the Placebo. The p-values, Least Squares means, differences between the LS treatment means and placebo, and 95% confidence intervals for the treatment differences will be computed. The summary of this analysis will be presented in Table 14.2.2.1.2 and Listings 16.2.6.6, 16.2.6.7 and 16.2.6.8.

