6.14.1.3 Weiss Functional Impairment Rating Scale – Parent Version (WFIRS-P)

WFIRS-P comprises 50 items grouped into six domains: Family, School (learning and behavior), Life Skills, Child's Self-Concept, Social Activities, and Risky Activities. The items relate to the past month and are scored using a 4-point (0, 1, 2 and 3) Likert scale. Higher WFIRS-P scores indicate more severe functional impairment. Missing items do not include omitted responses in the scoring (i.e., treat as "not applicable"). Each of the six domains is scored omitting items with a missing or 'not applicable' response. The WFIRS-P average score will be calculated over the 50 items as sum of all items with a response divided by total number of items that have been endorsed (e.g., do not include 'not applicable' items in the total). The same approach will be used for the subscores. The change from baseline in WFIRS-P to Week 8 (EOS) will be analyzed using ANCOVA model with fixed effects for treatment and baseline as a covariate. Missing Subscale scores and Total Score will be handled using multiple imputation under MAR assumption for inferential analyses. Each of the treatment groups (SPN-812 ER 200 mg and 400 mg) will be compared with the Placebo. The p-values, LS means of treatment groups, differences between the LS means and placebo, and 95% confidence intervals for the treatment differences will be computed. The summary of this analysis will be presented in Table 14.2.2.1.3 and Listings 16.2.6.9, 16.2.6.10 and 16.2.6.11.

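### The Gamma-regression fallback in SAP 6.13 is inadmissible for the change-from-baseline ANCOVAs as written, and its response, link and trigger are not defined

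*SAP*

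**What the plan says.** SAP section 6.13 sets a general rule for Analysis of Covariance: "the Gamma regression will be used on the original scale, if the normality assumption for the standard ANCOVA model is not met". The decision is "based on diagnostic residual plots based on the data before imputation". The section names no link function, no treatment contrast and no criterion for reading the plots. It does not say what the original scale is, or whether the decision is taken before unblinding.

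Section 4 (definition 3) defines change from baseline as "observed value at that Visit minus observed value at baseline".

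The ANCOVA responses are:

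- **Conners 3-PS** (6.14.1.2, key secondary): "the change from baseline to Week 8 (EOS) in the composite T-score will be analyzed using ANCOVA model". Section 6.14.2.4 repeats this analysis for the self-report form.
- **WFIRS-P** (6.14.1.3, key secondary): "The change from baseline in WFIRS-P to Week 8 (EOS) will be analyzed using ANCOVA model".
- **PSI-4-SF** (6.14.2.2) and the **ADHD-RS-5 subscales** (6.14.2.3): also change from baseline.
- **Placebo-based multiple imputation sensitivity analysis** (6.13.2): ANCOVA of the change in ADHD-RS-5 total score.
- **CGI-I** (6.14.1.1, first key secondary): "The absolute value of CGI-I at week 8(EOS) will be analyzed using ANCOVA with treatment as a fixed classification variable". This is not a change score.

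The primary analysis (6.13.1) is an MMRM, which the ANCOVA rule does not reach.

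**The concern.** The Gamma distribution gives no probability to values at or below zero. On all the scales listed as change scores, a higher score is worse, so a subject who improves has a negative change and a subject who stays the same has a change of 0. The rule therefore prescribes a model that does not exist for most of the endpoints it covers.

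Conners 3 and WFIRS-P are the second and third steps of the ordered testing sequence in section 6.14.1. If the plots for either are read as non-normal, the plan leaves the team with no usable instruction. The model, the response and the effect measure would then have to be settled after the data have been seen, inside a sequence meant to control type I error.

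**Working it through.** **Inputs from the SAP.** Change is visit minus baseline (section 4). Conners 3 domain T-scores are held between 40 and 90 (6.14.1.2). WFIRS-P items score 0 to 3 and are averaged (6.14.1.3). PSI-4-SF has 36 items scored 1 to 5 (6.14.2.2). Each ADHD-RS-5 subscale has 9 items scored 0 to 3 (sections 4 and 5.1). For CGI-I, "Both CGI-S and CGI-I are rated on a 7-point scale of 1 to 7".

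**Plan's own figures.** The point disputes none. An exact two-sample t-test with effect size 0.547 gives 90.3% power at 72 per group, and 72/(1 - 0.279) = 99.9, so 72 and 100 per group reproduce. They serve below only as simulation sizes.

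**Step 1: possible values against the Gamma requirement (y > 0).**

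| ANCOVA endpoint | Response in the SAP | Range of that response | Gamma as written | Raw-score range | Gamma on raw score |
|---|---|---|---|---|---|
| CGI-I | absolute value | 1 to 7 | possible | 1 to 7 | possible |
| Conners 3 composite | change | -50 to 50 | inadmissible | 40 to 90 | possible |
| WFIRS-P average | change | -3 to 3 | inadmissible | 0 to 3 | fails at 0 |
| PSI-4-SF total | change | -144 to 144 | inadmissible | 36 to 180 | possible |
| ADHD-RS-5 subscale | change | -27 to 27 | inadmissible | 0 to 27 | fails at 0 |
| ADHD-RS-5 total (sensitivity) | change | -54 to 54 | inadmissible | 0 to 54 | fails at 0 |

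The change ranges are raw maximum minus raw minimum in each direction, for example 90 - 40 = 50 and 180 - 36 = 144.

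**Step 2: how many values would be at or below 0.** The SAP gives no means or SDs for these changes, so this is a range under assumption. With normal changes, the share at or below 0 is Phi(-mean/SD).

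- mean/SD = -0.2: Phi(0.2) = 58%
- mean/SD = -0.5: Phi(0.5) = 69%
- mean/SD = -1.0: Phi(1.0) = 84%
- mean/SD = -1.5: Phi(1.5) = 93%

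The conclusion does not depend on the share, because a few such values are enough to break the likelihood.

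**Step 3: trial fits.** Gamma models with a log link were fitted to simulated data, 72 per arm, with assumed means and SDs. On change scores, estimation was infeasible for Conners 3 (68% to 90% of values at or below 0), WFIRS-P (69%) and PSI-4-SF (69%). The fit converged for CGI-I, raw Conners 3 and raw PSI-4-SF. For raw WFIRS-P with 6% exact zeros the log-likelihood was not finite.

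**Step 4: the raw-score reading against the rest of the SAP.** Sections 6.14.1.2 and 6.14.1.3 promise differences in LS means with 95% confidence intervals, and section 6.14.1 states its null hypotheses as no difference in treatment means. A Gamma model with a log link estimates a ratio of means. Section 6.14 also sets imputed values that fall below a scale to the scale minimum, which is 0 for WFIRS-P and the ADHD-RS-5 subscales. The plan's own imputation can therefore create the zeros that the model cannot take.

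**Step 5: is a rescue needed?** ANCOVA was simulated on complete data with exponential residuals (skewness 2) and no treatment effect, at 72 and 100 per arm. The type I error across runs was 4.8% to 5.3%, against a nominal 5%.

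**The case against.** The strongest reply is that the original scale plausibly means the raw score. Section 6.13 names its variables as scores, and section 6.14 imputes the Week 8 value within the range of the scale. On that reading Gamma fits Conners 3 and PSI-4-SF, and fails on WFIRS-P and the ADHD-RS-5 scores only for subjects at exactly 0. This stands as far as it goes. The SAP does not state that reading, however, and the reading conflicts with the change-score responses and the promised mean differences.

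A reader might infer that every ANCOVA in the plan has an unusable fallback. The documents do not support that: CGI-I is an absolute score with a minimum of 1. What remains for CGI-I is the undefined link and the lack of a criterion for reading the plots.

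A reader might also infer that improvers would be silently discarded and the estimand changed as well. These belong to different readings. A fit to change scores that fails is a visible event and changes no estimand; a fit to raw scores drops no improvers. The SAP specifies no software behaviour that would show values being dropped, and section 1 requires deviations to be identified and justified in the study report.

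Checking residuals before imputation is defensible and is not an error. The simulated type I error covers one shape of non-normality in complete data; it says nothing about power or the multiply imputed analysis.

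**Conclusion.** The point holds in limited form. For every ANCOVA whose response is change from baseline, the Gamma fallback is inadmissible as written; this follows from the SAP's definition of change and needs no assumption about effect size. The raw-score reading makes the model possible for Conners 3 and PSI-4-SF, but it replaces the stated response, may replace the stated effect measure, and still fails at zero for WFIRS-P and the ADHD-RS-5 subscales. For all ANCOVA endpoints, including CGI-I, the switch rests on plots with no stated criterion.

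The primary MMRM result is not at stake. Exposure is greatest for Conners 3 and WFIRS-P, two of the three key secondary endpoints, and only if the plots are read as non-normal. The 58% to 93% shares rest on assumed standardised mean changes. The wording should be corrected before database lock.

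**What to change.** Delete the Gamma sentence from section 6.13. State that the specified ANCOVA on the multiply imputed data is the sole inferential analysis for the key secondary endpoints and the other ANCOVA endpoints.

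If a check on non-normality is wanted, pre-specify one supportive analysis that is valid for change scores: ANCOVA with heteroscedasticity-robust standard errors, or rank ANCOVA. State that it does not replace the main result.

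The cost is one sentence of SAP wording and at most one extra supportive table. No new data and no change in sample size are needed.

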6.13.1 Analysis of Primary Endpoint

The primary efficacy variable, change from baseline in ADHD-RS-5 Total Score to Week 8 (EOS), will be analyzed using a Mixed Model for Repeated Measures (MMRM), which assumes that missing data are missing at random (MAR). The model will include fixed effect terms for baseline ADHD-RS-5 Total Score, age group, treatment, visit, and treatment-by-visit interaction as independent variables. The model parameters will be estimated using restricted maximum likelihood method with unstructured variance-covariance matrix and Kenward-Roger approximation to estimate denominator degrees of freedom. In case there is a convergence problem in the MMRM model with the unstructured variance covariance matrix, the first (co)variance structure which does not have convergence problem will be used for the analysis from the following ordered list: 1) Toeplitz 2) Autoregressive of order 1 3) Compound symmetry.

The adjusted mean (LS Mean) of CFB to EOS for ADHD-RS-5 Total Score for each treatment group (Placebo, SPN-812 ER 200 mg and SPN-812 ER 400 mg) will be presented, along with the corresponding standard error. Each of the treatment groups (SPN-812 ER 200 mg and 400 mg) will be compared with the Placebo. The p-values, Least Squares (LS) of treatment means, differences between the LS treatment means and placebo, and 95% confidence intervals for the treatment differences will be computed.

To maintain the Type I error rate at 5% level, a sequential testing ([Westfall et al 1999](#)) of the null hypotheses H_{01} : No treatment mean difference between SPN-812 ER 400 mg group and placebo group and H_{02} : No treatment mean difference between SPN-812 ER 200 mg group and placebo group

will be performed. If H_{01} is not rejected, then H_{02} will not be tested and the conclusion will be that neither dose groups are efficacious. If H_{01} is rejected, then H_{02} will be tested. If H_{02} is rejected then it will be concluded that both SPN-812 ER 400 mg and SPN-812 ER 200 mg are superior to placebo. If H_{01} is rejected and H_{02} is not rejected then it will be concluded that only SPN-812 ER 400 mg is superior to placebo.

The summary of primary analysis will be presented in Table 14.2.1.1.

The corresponding MMRM SAS output will be presented in Listing 16.1.9.1. The ADHD-RS-5 questionnaire, total, subscale scores, and derived ADHD rating scale - 5 (behaviors and scores) and binary variables will be listed in Listings 16.2.6.1 and 16.2.6.2 and 16.2.6.3.1 and 16.2.6.3.2.

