3.1 Study Design

This is a multicenter, randomized, double-blind, placebo-controlled, 3-arm, parallel-group study, to assess the efficacy and safety of SPN-812 ER as monotherapy for the treatment of children 6-11 years old with ADHD. Approximately 300 subjects will be randomized in a 1:1:1 ratio of placebo or one of the two active treatment arms (SPN-812 ER 200 or 400 mg). Following up to four weeks of screening, subjects will be randomized and undergo three weeks of titration followed by five weeks of maintenance for a total of eight weeks of treatment and total study duration of up to 12 weeks. The study schematic appears in [Figure 1](#).

Figure 1: Design Schematic

Titration to SPN-812 ER 200 mg dose from baseline (Day 1) in the week 1 visit for subjects randomized to SPN-812 ER 200 mg dose by 100 mg. Titration to SPN-812 ER 200 mg, 300 mg, and 400 mg dose from baseline (Day 1) in the week 1, week 2, and week 3 visits, respectively, for subjects randomized to SPN-812 ER 400 mg dose by 100 mg each week.

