The ADEFF1 analysis dataset will be used for programming the primary analysis table and will contain variables for Subject ID, BASE (Baseline (Visit 2)), AVAL (values at Visit 3 –Visit 10), CHG (for CFB), ITT Flag variable, Treatment, and other necessary variables to be created. For each subject there will be nine records associated with nine visits: Baseline and Visit 3 - Visit 10. The ADEFF2 analysis dataset will be created based on MI assuming MNAR for sensitivity analysis and MI assuming MAR for secondary analyses. The ADEFF2 will contain 100 imputations of each record of each visit for the variables in ADEF1 with IMPUTNR variable.

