6.13.2 Sensitivity Analysis

The sensitivity analysis assumes that missing ADHD-RS-5 Total Scores are missing not at random (MNAR), that is, the probability that an observation is missing may depend on its underlying unobserved value. (For example, the probability of missing ADHD-RS-5 Total Score at Week 8 is not related to the observed ADHD-RS-5 Total Score at visit 9). Placebo-based multiple imputation will be used to fill in missing values. This approach may be considered “worst-case” sensitivity analyses as it assumes that after discontinuation, subjects from the active treatment arms would adopt the outcome model estimated from the placebo arm. The placebo-based imputation will be implemented by adopting the following three steps.

- 1) SAS PROC MI (SEED=220877) is applied to the input dataset containing all by-visit ADHD-RS-5 Total Score during the baseline, titration, and maintenance period. Multivariate imputation will be carried out by the fully conditional specification (FCS) method. One hundred (100) multiply-imputed datasets will be created. SAS® PROC MI with the MNAR statement will be implemented by using the following SAS code.

```
PROC MI DATA= EFF NIMPUTE=100 SEED=220877 OUT=MNAROUT
  CLASS TREATMENT;
  VAR BASE WK1– WK8(EOS);
  FCS REG;
  MNAR MODEL (BASE WK1– WK8 (EOS))/MODELOBS= (TREATMENT='A');
  RUN;
```

In the above SAS code, EFF denotes the efficacy data set, Base, WK1– WK8 are analysis values of ADHD-RS-5 total at baseline and each of treatment weeks from Week 1 (at Visit 3) to Week 8 (at Visit 10), and treatment = ‘A’ denotes Placebo.

2. For each of the multiply-imputed data sets, CFB to EOS will be computed. For each imputation, the CFB will be analyzed using ANCOVA model, which will include fixed effect terms for treatment and baseline ADHD-RS-5 Total Score as a covariate. Each of the treatment groups (SPN-812 ER 200 mg and 400 mg) will be compared with the Placebo. The LS means of treatment groups, differences between the LS means of treatment groups and placebo, 95% confidence intervals around the differences and p-value will be computed.
3. Finally, to combine estimates (LS means, treatment LS mean differences, 95% CI around the difference and p-value) from the 100 datasets, SAS® PROC MIANALYZE will be used.

The summary of sensitivity analysis will be presented in Table 14.2.1.2. The corresponding full SAS output will be presented in Listing 16.1.9.2.

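### The primary MMRM fits one baseline slope to all eight visits although only Week 8 is tested; a baseline-by-visit term would be a nearly free safeguard for precision and, under uneven dropout, against bias.

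*SAP*

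**What the plan says.** Section 6.13.1 defines the mean model of the primary analysis: "The model will include fixed effect terms for baseline ADHD-RS-5 Total Score, age group, treatment, visit, and treatment-by-visit interaction as independent variables". It is fitted by "restricted maximum likelihood method with unstructured variance-covariance matrix and Kenward-Roger approximation". No baseline-by-visit term appears there or elsewhere in the SAP.

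Section 6.1 describes the dataset for this model: "For each subject there will be nine records associated with nine visits: Baseline and Visit 3 - Visit 10". That leaves eight post-baseline visits, Weeks 1 to 8, sharing one baseline coefficient. The inference concerns change to Week 8 for 400 mg and then 200 mg against placebo.

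The sensitivity analysis in Section 6.13.2 is built differently. After imputation, "the CFB will be analyzed using ANCOVA model, which will include fixed effect terms for treatment and baseline ADHD-RS-5 Total Score as a covariate". That is a single-visit model, so its baseline slope belongs to Week 8.

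**The concern.** The outcome is change from baseline, so its slope on baseline equals the slope of the raw score on baseline minus 1. If early scores follow baseline closely and later ones less so, this slope becomes more negative over the trial. The first three weeks are titration and the last five are maintenance (Sections 3.1 and 3.4.3), so a constant slope is a real assumption. The unstructured matrix does not relax it: it frees the residual covariance, not the mean.

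Two things could follow at Week 8. First, a misfitting slope leaves explainable baseline variation in the residual, which widens the standard error. Second, if the children still observed at Week 8 differ in baseline severity between arms, the misfit no longer cancels in the treatment difference. Section 6.6.1 justifies MMRM by its conditioning on earlier observations and on covariates related to missingness and outcome. Baseline severity is an obvious such covariate, and Section 3.5 expects 27.9% of children not to complete.

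**Working it through.** **1. The plan's own figure.** Section 3.5 sizes the trial "using a two-sample t-test with equal allocation to the treatment" groups, at two-sided 5% and 90% power. On the effect: "This assumes an effect size of 0.547, observed in the comparison of SPN-812 200 mg and placebo".

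- Normal approximation: n = 2 × (1.960 + 1.282)² / 0.547² = 70.2, so 71 per arm.
- Noncentral t: power is 0.899 at 71 and 0.903 at 72, so 72 is correct.
- Dropout: 72 / (1 − 0.279) = 99.9, so 100 per arm and 300 in total.

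The figure reproduces. It takes no credit for baseline adjustment, so it does not depend on the term at issue.

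**2. What must be assumed.** The SAP gives no baseline SD, no baseline-to-visit correlations and no dropout pattern by severity or arm. The check assumed:

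- baseline SD 6, and residual SD rising from 6 at Week 1 to 12.5 at Week 8;
- lag-1 residual correlation 0.85 (0.7 and 0.9 also run);
- monotone dropout of about 27.9%, with log-odds of 0.4 or 0.8 per baseline SD where it depends on baseline;
- true Week 8 difference −7.0 (0.547 × 12.8).

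An unstructured MMRM was fitted with and without baseline-by-visit, in 1,000 simulated trials of 300 per scenario and in large samples of 60,000. A t cut-off of 1.97 stood in for Kenward-Roger.

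**3. Precision, completely random dropout (one slope → by-visit slope).**

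| Slope of change on baseline, Week 1 → Week 8 | Mean model SE | Ratio | Power |
|---|---|---|---|
| −0.3 → −0.3 | 1.977 → 1.978 | 1.000 | 94.4% → 94.1% |
| −0.1 → −0.4 | 1.995 → 1.979 | 1.008 | 94.5% → 94.8% |
| −0.1 → −0.7 | 2.039 → 1.977 | 1.031 | 92.1% → 94.0% |
| 0 → −0.9 | 2.125 → 1.980 | 1.073 | 89.3% → 92.1% |

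In the last row the empirical SDs of the estimates give 2.164 / 2.050 = 1.056, so about 6% is a fair summary. The simulation error of each power is about √(0.94 × 0.06 / 1000) = 0.75 points, so the first two rows show no difference.

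In the large samples, with dropout depending on baseline equally in all arms, the SE excess was 0.5-0.8% for −0.1 → −0.4 and 2.1-3.6% for −0.1 → −0.7. In children: 1.005² = 1.010 and 300 × (1 − 1/1.010) ≈ 3; 1.036² = 1.073 and 300 × (1 − 1/1.073) ≈ 20.

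A separate large-sample GLS calculation used baseline SD 6.5, Week 8 SD 12.5, and raw-score slopes falling from 0.80-0.90 at Week 1 to 0.60-0.30 at Week 8. It gave Week 8 variance ratios of 1.006 to 1.073, an SE excess of 0.3% to 3.6%. The two agree.

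**4. Bias.** Roughly, the error is the Week 8 slope misfit times the between-arm difference in mean baseline among those still observed. Both factors must be non-zero. Absolute shift of the Week 8 difference, in points:

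| Dropout depends on baseline | Slope drift 0.3 | 0.6 | 0.9 |
|---|---|---|---|
| equally in every arm | ≤ 0.01 | ≤ 0.01 | 0.01 |
| in placebo only | 0.12-0.33 | 0.25-0.57 | 0.8 |
| in opposite directions by arm | 0.24-0.60 | 0.49-1.04 | 1.5 |

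Drifts 0.3 and 0.6 come from the large samples and 0.9 from the trial-sized runs. With equal dependence, the trial-sized runs differed by at most 0.03, within simulation noise. The sign reversed with the drift: under the same dropout patterns, −0.1 → −0.4 enlarged the apparent benefit and −0.4 → −0.1 reduced it. With the interaction, bias was within 0.09 points of zero throughout, against a simulation error of about 2.0 / √1000 = 0.06.

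**5. Effect on the test.** The two-sided error is Φ(−1.96 + s) + Φ(−1.96 − s), where s = shift / SE:

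- 0.5 / 2.0 gives 5.7%;
- 1.0 / 2.0 gives about 8%;
- 1.5 / 2.1 gives about 11%.

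The last two need steep drift with strongly unequal dropout.

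**The case against.** The strongest reply is that this is a preference. The primary model is fully specified and consistent in itself, with an ordered fallback list for the covariance. Leaving out the interaction does harm only if the slope really changes, and nothing in the SAP shows that it does. With equal slopes nothing is lost. With moderate drift the loss is small, and the sample size never relied on it. All of that stands. It limits the size of the point, but it does not make the constant-slope model preferable, since the alternative costs almost nothing.

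The interaction is not free in every scenario. With strongly arm-specific dropout and flat or mildly drifting slopes, the one-slope SE was equal or up to about 1% smaller (for flat slopes, 1.981 against 2.007, power 93.9% against 93.3%). That is a small price.

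Section 6.1 assigns early-termination visits to Visit 10 for statistical summaries. If that also governs the primary dataset, fewer Week 8 values are missing and the bias figures above would change.

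A reader might also infer that the omission is what separates the primary from the sensitivity analysis. That is only partly so. Section 6.13.1 includes age group and the Section 6.13.2 ANCOVA does not, so the two models would still differ after the change. The per-protocol ANCOVA does not help as a Week 8 comparator either, because the Supplementary Analyses section labels its endpoint Week 7 (EOS).

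**Conclusion.** The point holds in conditional form, as a free improvement. One baseline slope is imposed on eight visits although only Week 8 is tested. If the slope drifts, the Week 8 SE is larger by about 0.5-3.6% for moderate drift and about 6% in an extreme case, where power falls by about 3 points. If baseline-related dropout also differs by arm, the Week 8 difference can shift by a few tenths of a point or more. Every size here is illustrative and rests on the assumptions listed.

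Three stronger readings are tempting and not supported:

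- That the primary analysis uses the wrong slope and necessarily loses precision. The SAP contains nothing on how the slope behaves over visits.
- That dropout related to baseline severity is enough to bias the result. With the same relation in every arm, the two models agree.
- That the bias favours the drug. Its sign depends on the direction of drift.

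Nor does the point touch the sample size, which reproduces.

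**What to change.** In Section 6.13.1, add a baseline ADHD-RS-5 Total Score-by-visit interaction to the fixed effects before database lock. Keep the unstructured covariance, Kenward-Roger and the Week 8 contrasts as they are.

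The cost is one term in the text and in the PROC MIXED code, and 8 − 1 = 7 extra fixed-effect parameters, with no new data. With 300 children the simulations show no visible loss under random dropout, and at most about 1% of the SE under strongly arm-specific dropout. If the primary model is to stay unchanged, the lesser step is to prespecify the version with the interaction as a sensitivity analysis.
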